#### Background Spectacle independence is a central aim in modern cataract surgery. Although bilateral monofocal IOL implantation, aiming for emmetropia or low myopia, leads to high levels of patient satisfaction in distance vision, spectacle dependence for reading and other near vision tasks is the usual result. One technique available to surgeons to reduce spectacle dependence is to use multifocal IOL. With increasing demands for complete spectacles independence from patients after cataract surgery, multifocal IOLs have been introduced widely in cataract surgery. This should result in less spectacle dependence for patients.

Residual astigmatism after cataract surgery can influence the post operative outcome of multifocal IOLs and lead to to poor visual performance of the multifocal lenses. Hence it is important to correct the astigmatism during cataract surgery to get the optimal result with Multifocal IOLs. Currently patients with high degrees of corneal astigmatism are denied multifocal lenses and in patients with low degrees of corneal astigmatism the option offered is attempting to correct the corneal astigmatism with corneal incisional surgery such as limbal relaxing incisions.

Combining a multifocal optic with a toric optic that corrects corneal astigmatism, so called multifocal toric lenses would correct the corneal astigmatism more precisely and therefore make the patient as much as possible spectacle independent. Results with toric IOLs (without a multifocal component) have achieved very good astigmatic control. Precise alignment of the cylindrical axis of the IOL with the astigmatic axis of the cornea is key for success.

The alternative method to reduce corneal astigmatism as part of cataract surgery is to make relaxing incisions (cuts) on the steeper axis of the cornea. This technique is in use since more than 2 decades and is widely used in clinical routine. As with toric IOLs, precise alignment of the cuts with the axis of astigmatism is essential. The disadvantage of the incisional techniques is the variability of the effect between patients since it depends on factors such as the extent of scarring of the cuts after surgery as well as corneal thickness and shape. Also, there may be a tendency for regression of the effect during the first 9 months after surgery. Furthermore there is a small risk of infection of the corneal incision and microbial keratitis after limbal relaxing incision has been described. The main advantage is the low cost.

Study objectives	Purpose of the present study is to compare the outcome of multifocal toric intraocular lens with standard multifocal lens plus incisional surgery in patients undergoing bilateral cataract surgery			
Study design	Randomised controlled trial with intra-patient comparison			
Study population	60 eyes (30 patients) with cataract and corneal astigmatism of 1.00 to 2.50 D			
Investigational Product (Medical Device)	First eye to be operated: Multifocal toric IOL (Rayner, UK), or LRI with 600µm knife according to the Donnenfeld nomogram + Multifocal IOL (Rayner, UK).			
	The contralateral eye will receive the alternative treatment			
Main outcome variables	
 
Composite scoring of unaided distance and near vision (monocularly)
 
			
	
 
Residual astigmatism evaluation by Subjective Refraction and autorefraction (Topcon)
 
			
	Any intraoperative or postoperative complications			
Additional outcome	Simulated K-readings using corneal topography (Pentacam)			

variables

Rotational stability of the IOL - angle of axis as measured from retroillumination photographs: Orientation [degrees]

- Dysphototpsia and satisfaction/ questionnaire monocularly
- Reading speed Salzburg reading test monocularly
- Glare testing monocularly(Oqas)

1		7
1.1	Background	7
1.2	Rationale	9
1.3	Risk/benefit assessment	9
2	STUDY OBJECTIVE	
3	INVESTIGATIONAL PLAN	
3.1	Design	
3.2	Selection of study population	
3	3.2.1 Number of subjects	
3	3.2.2 Pre-study screening	
3	3.2.3 Inclusion criteria	
3	3.2.4 Exclusion criteria	
3.3	Investigational Product (Medical Device)	
3	3.3.1 Medical Device (IOL) used in the study	

### 1 Introduction

### 1.1 Background

Spectacle independence is a central aim in modern cataract surgery. Although bilateral monofocal IOL implantation, aiming for 0.00 to -0.50D, leads to high levels of patient satisfaction, spectacle dependence for reading and other near vision tasks is the usual result. Most surgeons faced with a patient with bilateral cataract would leave them either emmetropic or with very low levels of post-operative myopia in both eyes. This leaves most patients dependent on spectacles for near visual tasks.

One technique available to surgeons to reduce spectacle dependence is to use a multifocal IOL. Recent diffractive IOL designs have improved spectacle independence while reducing the glare phenomena(1)(6). A European study of the Restor diffractive IOL found that 74.4% never wore spectacles, glare and haloes occurred in 8.5% and 4.2% of patients respectively and 95.7% of patients said that they would have the same implant again(2). Only one patient out of 127 had the IOL explanted because of glare and haloes. FDA data for the Restor reported a spectacle independence figure of 80% (www.fda.gov/cdrh/pdf4/p040020.html). Bilateral implantation with contemporary multifocal lens implants reduce spectacle dependence and is well tolerated; but it involves compromise for the quality of distance vision. Residual astigmatism after cataract surgery can influence the post operative outcome and lead to poor performance of these lenses (3). Hence it is important to correct the astigmatism during cataract surgery to get the optimal result with Multifocal IOLs. The options available to correct astigmatism is either to implant a multifocal toric IOL or make limbal relaxing incisions combined with a multifocal IOL.

With increasing demands of patients concerning refractive outcome after cataract surgery, toric IOLs that correct corneal astigmatism have been introduced more widely to cataract surgery. Originally toric IOLs were used mainly for patients with high degrees of astigmatism, especially after corneal surgical procedures such as penetrating keratoplasties. Recently, toric IOLs are available from numerous manufacturers to correct lower amounts of astigmatism which are much more prevalent. This should result in less spectacle dependence of patients due to the precise nature of the astigmatic correction (4).

The new multifocal toric lenses combine the separate optical features of a standard multifocal lens and the toric lens to provide a superior multifocal outcome with precise and sustainable toric correction.

The alternative method to reduce corneal astigmatism as part of cataract surgery is to make relaxing incisions (cuts) on the steeper axis of the cornea. This technique is in use since more than 2 decades

and is widely used in clinical routine(5). As with toric IOLs, precise alignment of the cuts with the axis of astigmatism is essential. Nomograms for these astigmatism correcting incisions are available depending on the extent and the orientation of astigmatism and the age of the patient. The disadvantage of the incisional techniques is the variability of the effect between patients since it depends on factors such as the extent of scarring of the cuts after surgery as well as corneal thickness and shape. Also, there is a tendency for regression of the effect during the first 9 months after surgery. Furthermore there is a risk of infection of the corneal incision and microbial keratitis after limbal relaxing incision has been described. The main advantage is only the low cost.

Concerning alignment, the axis is defined by either corneal keratometry or topography, or both. Misalignments may be caused intra- or postoperatively. Intraoperatively, misalignment may happen due to cyclotorsion of the eye in the lying position or due to local anaesthesia, and due to imprecision of positioning of the IOL in the bag or of placing the astigmatism correcting incisions on the cornea. These imprecisions can be dealt with by preoperative marking of the eye in the sitting position and use of meticulous positioning of the IOL or incisions during surgery.

A Rayner single-piece open-loop IOL made of hydrophilic acrylate was shown to have a good haptic memory and is thought to adhere to the capsule resulting in little to no rotation after surgery. A toric optic design has been added to this multifocal IOL design.

One of the front and back surfaces of the lens defines a toric surface for an astigmatic optical correction, and one of the front and back surfaces, which can be the same surface or the opposite surface, defines a multifocal surface for a presbyopic optical correction, to provide visual acuity for astigmatic presbyopes

There is currently a study being conducted at Moorfields Eye Hospital comparing monofocal lenses with LRI surgery versus toric monofocal lenses. However this does not compare with the current proposal as in multifocal IOL surgery astigmatism control is definitively more important than in monofocal IOL surgery. The presence of residual postoperative astigmatism after multifocal IOLs cataract surgery is not advisable and most of the companies making multifocal IOLs advise not to operate on patients with more than 2.00 diopters of astigmatism and advocate minimizing astigmatism by means of incisional corneal surgery at the time of the cataract surgery.

Residual post-operative astigmatism leads to poor performance of multifocal lenses. One reason is that multifocal IOLs do reduce significantly contrast sensitivity especially in some light condition and adding astigmatism does have a negative impact in further reducing contrast sensitivity. Furthermore, the presence of astigmatism makes the multifocal generated near , intermediate and distance images more blurred and thus makes the brain process of learning to focus on a given image for near, intermediate and distance much more difficult for the patient.

Toric multifocal IOLs are the latest multifocal IOLS generation and do have the huge potential of massively improve the outcome of multifocal IOL surgery hence the relevance of this exploratory study. Finally whilst a monofocal toric IOL does have only a toric surface the multifocal toric IOL does have a more complex construction incorporating the multifocal and toric surfaces on one single IOL and hence comparison in terms of astigmatism reduction between the monofocal and multifocal IOLs may not be meaningful since a new variability is introduced with the multifocal toric IOL.

We plan to compare the visual performance and outcome of the non toric multifocal IOL combined with corneal incisional surgery to correct astigmatism with a toric multifocal IOL alone.

# 1.2 Rationale

To assess the efficacy of multifocal IOL with corneal pre-existing astigmatism and compare the outcomes of a multifocal toric IOL or a standard multifocal IOL combined with limbal relaxing incisions.

# 1.3 Risk/benefit assessment

Safety: both IOL used are CE approved and toric monofocal is well estabilished already. One of the major problems of all studies with multifocal IOL is astigmatism correction. Hence the incorporation of toric component to the multifocal IOL should result in a better performance of the multifocal IOL in patients with corneal astigmatism.

The investigation will show whether multifocal toric IOLs are superior to corneal incisional surgery plus standard multifocal IOL that is readily used in clinical practise, in correcting astigmatism in patients with age-related cataract. This study will also show if correction of astigmatism with a toric multifocal IOL leads to better visual performance of the multifocal IOL. Since the IOL design studied is well known and has a long track record in the non-toric variant, and the non-invasive measuring procedures in this study are well tolerated, the benefit/risk ratio is acceptable. The contra lateral eye will receive limbal relaxing incisions with the multifocal IOL in the non-toric form. Since only patients that have low to moderate astigmatism are included in the trial, the difference in outcome should be small enough to not compromise binocular vision.

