# 2 Study objective

Purpose of the present study is to compare efficacy of multifocal IOL after correction of astigmatism with either implanting a multifocal toric IOL or implanting a standard multifocal IOL combined with limbal relaxing incisions.

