#### 4.6 Biometric methods

#### 4.6.1 Biometric methods - outcome variables

The outcome variables will be assessed using descriptive statistics.

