#### 4.7 Data Analysis and Use of study findings

We propose to generate a composite measure with 4 categories based on measures of distance and near visual acuity, but will use this pilot data (with patient questionnaire data) to determine how best to do this.

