#### Components of the Visual Scoring System

The findings of this pilot study will be published by the investigators in a scientific journal and presented at scientific meetings, and will be used to power a full-scale randomised controlled trial.

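### Section 1.3 promises to show whether the toric multifocal IOL is superior, but the protocol otherwise describes an exploratory pilot with descriptive analysis, which cannot give that verdict

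*Protocol*

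**What the plan says.** Protocol section 1.3 (Risk/benefit assessment) makes two statements about what the study will deliver. The first is "The investigation will show whether multifocal toric IOLs are superior to corneal incisional surgery plus standard multifocal IOL"; the rest of that sentence limits it to the correction of astigmatism in age-related cataract. The second is "This study will also show if correction of astigmatism with a toric multifocal IOL leads to better visual performance of the multifocal IOL".

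The other sections are more modest:

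- Section 1.2 aims to "compare the outcomes of a multifocal toric IOL or a standard multifocal IOL combined with limbal relaxing incisions".
- Section 2 says "Purpose of the present study is to compare efficacy of multifocal IOL after correction of astigmatism".
- Section 1.1 ends its case for the toric multifocal lens with "hence the relevance of this exploratory study".
- Section 4.6.1 gives the whole analysis of outcomes in one sentence: "The outcome variables will be assessed using descriptive statistics".
- Section 4.7 proposes a four-category composite of distance and near acuity, and says the investigators "will use this pilot data (with patient questionnaire data) to determine how best to do this".
- Under the heading Components of the Visual Scoring System, the findings of the pilot "will be used to power a full-scale randomised controlled trial".

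The design (sections 3.1 and 3.2.1) is randomised, with one eye of each of 30 patients receiving each treatment. The main outcomes (section 3.5.1) are the composite of unaided distance and near vision, residual astigmatism by subjective refraction and autorefraction, and complications.

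**The concern.** Section 1.3 tells the reader that the study will answer two comparative questions. A study that answers whether one treatment is superior needs a rule for reaching that answer. This protocol states descriptive summaries instead, and describes the study's use as preparation for the trial that would give the answer. The two accounts do not fit together.

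What is at stake is how the result is read. If 1.3 stands, it could be cited to present a favourable descriptive difference as proof of superiority. It could equally be cited to present a small or absent difference as proof that the lenses perform alike. Neither conclusion would follow from the analysis that the protocol states.

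**Working it through.** **1. The statements side by side**

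| Question | Section 1.3 | Elsewhere in the protocol |
|---|---|---|
| Aim | show whether superior; show if performance is better | compare (1.2, 2) |
| Status of the study | not qualified | exploratory (1.1); pilot (4.7 and Components of the Visual Scoring System) |
| Analysis | none named | descriptive statistics (4.6.1) |
| Use of the findings | an answer on superiority | powering a full-scale trial |

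The conflict lies between statements that the protocol itself makes. It does not depend on a test, alpha or power calculation being absent, since an SAP that is not shown could hold those.

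**2. The two promises are not equally exposed**

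- *Correcting astigmatism.* Residual astigmatism is a named main outcome with stated measurement methods (section 4.1), in a randomised paired design. The quantity is defined. What is lacking is an analysis that yields a verdict.
- *Visual performance.* The scoring table printed within section 4.4 already fixes grades A to D for distance and for near acuity. Section 4.7 leaves open how to combine them and will settle that from these data. A verdict on the composite would therefore use a score chosen after the results are seen. Unaided acuity, reading speed, contrast and glare are measured separately and do not share this weakness.

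**3. What 30 pairs can do**

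The protocol states no alpha, power, target difference or SD, so it has no figure to reproduce. The figures below assume 30 complete pairs and a two-sided 5% level, in units of the SD of the within-patient difference.

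- Half-width of the 95% CI = t(29; 0.975)/√30 = 2.045/5.477 = 0.373 SD.
- Difference detectable with a paired t-test (exact power): 0.53 SD at 80% power and 0.61 SD at 90%. The normal approximation gives (1.960 + 0.842)/√30 = 0.51 SD for 80%.
- Chance that the 95% CI excludes zero, by true difference:

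| True difference (SD) | 0.2 | 0.3 | 0.4 | 0.5 | 0.6 | 0.8 |
|---|---|---|---|---|---|---|
| Chance | 19% | 36% | 56% | 75% | 89% | 99% |

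In dioptres, if the SD of the paired difference in residual astigmatism were 0.4 to 0.8 D (an assumption, not a protocol figure), the half-width would run from 0.373 × 0.4 = 0.15 D to 0.373 × 0.8 = 0.30 D.

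These figures show that the study can estimate the difference. Because the protocol gives neither a target difference nor an SD, they cannot show where in the table the study lies.

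**The case against.** The strongest reply is that this is loose wording in an introductory section. The formal rationale and objective say only that the treatments will be compared, and the protocol tells the reader plainly that a full-scale trial is to follow. That is fair, and it keeps the severity low. It does not remove the conflict, because 1.3 makes the opposite statement without qualification.

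Several stronger readings are tempting, and the protocol does not support them:

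- *The benefit/risk judgement rests on the superiority claim.* A reader might infer this from where the sentences stand. In fact 1.3 bases its conclusion on the history of the lens design and the tolerability of the measurements. Section 4.8 names the chance of spectacle independence as the benefit to patients.
- *Thirty patients are too few.* The working does not show this. A paired study of 30 has reasonable power for differences of about 0.5 to 0.6 SD or more, and a pilot need not be powered at all.
- *The composite is undefined.* Cut-offs for its components exist; only the way of combining them is open.
- *Descriptive analysis is wrong.* It is legitimate for a pilot, and section 4.6.1 does not rule out a paired summary. Detail such as between-eye correlations or the handling of near-acuity grades can be left to the SAP.

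**Conclusion.** The point holds as an inconsistency between what section 1.3 says the study will show and what the rest of the protocol sets out to do. An exploratory pilot that is analysed descriptively and meant to power a later trial can estimate the difference between treatments. As planned, it cannot deliver a verdict on superiority in correcting astigmatism or on better visual performance. The second promise is the weaker, but only insofar as it relies on the composite.

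The size of the fault is not numerical. The half-width of about 0.37 SD of the paired difference (30 complete pairs, 95% level) describes the precision the study offers and is no evidence that it is too small. Severity is minor to moderate: no estimate or safety conclusion changes, but the protocol claims a property that its stated analysis does not have.

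**What to change.** **Section 1.3.** Replace both sentences with, for example: *The investigation will estimate the within-patient difference between the multifocal toric IOL and limbal relaxing incisions plus a standard multifocal IOL, in residual astigmatism and in visual performance, to inform a full-scale trial. It is not designed to establish superiority.*

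**Section 4.6.1.** Add, for example: *For residual astigmatism (subjective refraction and autorefraction reported separately) and for monocular unaided distance acuity in logMAR, each at 3 months, the mean within-patient difference (toric eye minus LRI eye) will be reported with its SD and 95% CI. Results on the composite score are exploratory, because the score is settled from the same data.*

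This uses the pairing that the design already provides, and it gives the SD of the paired difference that a later intra-patient trial would need. The remaining summaries can stay with the SAP.

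If a verdict on superiority is truly intended, rewording is not enough. The protocol would then need one primary outcome, a hypothesis, a paired test and a justified sample size.

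**Cost.** A less ambitious claim in 1.3 and slightly more analysis of data already scheduled for collection. No extra patients, visits or measurements.

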# 2 Study objective

Purpose of the present study is to compare efficacy of multifocal IOL after correction of astigmatism with either implanting a multifocal toric IOL or implanting a standard multifocal IOL combined with limbal relaxing incisions.

# 3 Investigational plan

# 3.1 Design

Randomised controlled trial with intra-patient comparison (bilateral study)

# 3.2 Selection of study population

The participants will be selected by the clinical investigators

# 3.2.1 Number of subjects

60 eyes of 30 patients with bilateral cataract.

# 3.2.2 Pre-study screening

The following examination will be carried out in each patient before cataract surgery:

- A full ophthalmic examination including slit lamp biomicroscopy and retinal examination.

# 3.2.3 Inclusion criteria

- Bilateral cataract and be planning to have both eyes operated on.
- Age 21 and older
- Have cataracts that allow IOL master biometry
- Regular corneal astigmatism 1.00 up to 2.50 D
- Difference of corneal astigmatism in both eyes to be equal to or less than 0.75D
- written informed consent to surgery and participation in the study
- Speak English

# 3.2.4 Exclusion criteria

Any of the following will exclude a subject from the study:

Relevant other ophthalmic diseases such as: pseudoexfoliation, glaucoma, traumatic cataract corneal scars, and other co-morbidity that could affect capsule bag stability (e.g. Marfan syndrome)

- Irregular corneal astigmatism on Pentacam topography
   Surgery should be :
- Performed by consultants
- Second eye to be listed within 3-4 weeks whenever possible.

#### 3.3 Investigational Product (Medical Device)

The investigator will dispense the investigational product only to subjects included in this study.

All IOL supplies will be stored in accordance with the manufacturers' instructions.

Details of the exact date of IOL implantation will be documented in the case report form.

#### 3.3.1 Medical Device (IOL) used in the study

Toric Multifocal IOL (Rayner) – Model M-Flex T 588 or 638 - CE marked since January 2007 Non-toric Multifocal IOL (Rayner) – Model M-Flex 630F - CE marked since 2006 (in routine use)

